An O'Brien-Fleming alpha spending function will be used to specify the alpha level threshold for determination of treatment effect significance at each interim analysis and the final analysis. Using the percentage of patient years of follow-up as an approximation to the statistical information available at each analysis and assuming a one-sided, overall type I error rate of 2.5%, the one-sided significance thresholds are 0.0058, 0.0103, 0.0156, and 0.0190 for the first, second and third interim analyses, and the final analysis, respectively. Study success will be declared if the posterior probability that palovarotene reduces the annualized change in new HO volume is greater than 1 minus the one-sided significance threshold. For example, the posterior probability that palovarotene reduces the annualized change in new HO volume must be greater than 0.9810 to declare study success at the final analysis. A futility analysis was conducted for the second interim analysis based on the pre-specified criteria using square-root transformation and on additional analyses without the square-root transformation. Based on feedback received by the DMC following the second interim analysis, the futility analysis conducted at the third analyses will use the predefined model with and without square-root transformation to assess whether the study shows insufficient evidence of efficacy. If the efficacy criteria have not been met by the final analysis of Part A the study may be terminated.

---

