Accrual of 80 palovarotene-naïve subjects with the R206H ACVR1 mutation is expected to take place in approximately 10 months to 1 year and it is assumed that the full NHS dataset will be available at the first interim. The amount of statistical information at each interim analysis can be approximated by the sum of the follow-up in each study divided by the total expected. The total follow-up expected across the NHS and the MOVE Trial is 317.5 years (NHS: 45\*1.5 years + 45\*2.0 years; MOVE: 80\*2.0 years). Assuming eight subjects enrolled in the MOVE study per month, the percentage of patient follow-up for each analysis is 66%, 80%, and 92% at the first, second, and third interim analysis, respectively. Using these percentages, the alpha level threshold used to determine treatment effect significance at each analysis was derived using the Lan-DeMets alpha-spending function with O'Brien-Fleming parameterization and assuming a one-sided, overall type I error rate of 2.5%. The one-sided significance thresholds are 0.0058, 0.0103, 0.0156, and 0.0190 for the first, second, and third interim analyses, and the final analysis, respectively. Study success will be declared if the posterior probability that palovarotene reduces the annualized change in new HO volume is greater than 1 minus the one-sided significance threshold. For example, the posterior probability that palovarotene reduces the annualized change in new HO volume must be greater than 0.9810 to declare study success at the final analysis. A futility analysis was conducted for the second interim analysis based on the

pre-specified criteria using square-root transformation and additional analyses without the square-root transformation. Based on feedback received by the DMC following the second interim analysis, the futility analysis conducted at the third analyses will use the predefined model with and without square-root transformation to assess whether the study shows insufficient evidence of efficacy. If the efficacy criteria have not been met by the final analysis of Part A the study may be terminated. Stopping the study for futility will be considered if the posterior probability that  $\gamma < 0.7$  (at least a 30% reduction in annualized new HO volume on the square-root scale) is less than 5%. and taking into consideration additional analyses performed without the square-root transformation.

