Ninety-nine palovarotene-naïve subjects with the R206H ACVR1 mutation were enrolled into the current trial and are to be followed for 2 years. There were to be three early interim efficacy analyses and one final analysis. Futility was declared at the second interim analysis, but the study continued. The final analysis for Part A will occur when all subjects have completed 2-year follow-up. (Note that, as described, due to the prolonged palovarotene interruption prior to the completion of Part A, IA3 is designated the final analysis.)

The first interim analysis was to take place when approximately 35 MOVE subjects complete 1 year of follow-up with the second and third interim analyses occurring when all subjects in the Principal EP have the opportunity to have complete (i.e., have WBCT data) 12 months and then 18 months of follow-up, respectively. It was assumed that the full NHS dataset will be available at the first interim analysis. The amount of statistical information at each interim analysis can be approximated by the sum of the follow-up in each study divided by the total expected. The total follow-up expected across the NHS and the MOVE Trial is 317.5 years (NHS: 45*1.5 years + 45*2.0 years; MOVE: 80*2.0 years). Assuming eight subjects enroll in the MOVE study per month, the percentage of subject follow-up for each analysis is summarized in Table 7 where values with an asterisk indicate approximate information based on expected accrual rates and total planned accrual in the Principal EP.

Table 7. Observed MOVE Follow-up at Each Planned Analysis

Analysis	Observed MOVE follow-up	Percentage of follow-up available
Interim #1	35 subjects with 12 months *45 subjects with 6 months	66%
Interim #2	*80 enrolled subjects with 12 months *35 subjects with 18 months	80%
Interim #3	*80 enrolled subjects with 18 months *35 subjects with 24 months	92%
Final	80 enrolled subjects with 24 months	100%

Using these percentages, the alpha level threshold used to determine treatment effect significance at each analysis was derived using the Lan-DeMets alpha-spending function with O'Brien-Fleming parameterization and assuming a one-sided, overall type I error rate of 2.5%. The one-sided significance thresholds are 0.0058, 0.0103, 0.0156, and 0.0190 for the first, second and third interim analyses and the final analysis, respectively, in the scenario above.

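### The named spending function, the printed information fractions and the printed significance thresholds do not agree with one another

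*SAP*

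**What the plan says.** Three statements have to fit together.

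- **Method.** SAP 2.4.4 says the thresholds were "derived using the Lan-DeMets alpha-spending function with O'Brien-Fleming parameterization and assuming a one-sided, overall type I error rate of 2.5" per cent. Protocol 8.2 and 8.5.2.1 and SAP 1.7 name the same function. SAP 1.9.1 adds that the O'Brien-Fleming form replaced a Pocock form on FDA advice.
- **Fractions.** Protocol 8.5.2.1: "the percentage of patient follow-up for each analysis is 66%, 80%, and 92% at the first, second, and third interim analysis, respectively". SAP Table 7 prints the same three percentages. Information is "approximated by the sum of the follow-up in each study divided by the total expected", the total being 317.5 years ("NHS: 45*1.5 years + 45*2.0 years; MOVE: 80*2.0 years"). On the control side, "It was assumed that the full NHS dataset will be available at the first interim analysis".
- **Thresholds.** SAP 2.4.4: "The one-sided significance thresholds are 0.0058, 0.0103, 0.0156, and 0.0190". The Protocol Synopsis has the same four: "the one-sided significance thresholds are 0.0058, 0.0103, 0.0156, and 0.0190". Both documents turn the last one into a worked final success criterion, a posterior probability above 0.9810.

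Both documents say the thresholds were obtained from those percentages with that function.

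**The concern.** A reader who applies the named function to the printed percentages does not get the printed thresholds, and a reader who adds up Table 7 does not get all of the printed percentages. These numbers form the success rule for the primary endpoint.

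Three things depend on knowing which element is wrong:

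- whether the printed set holds 2.5%;
- which boundary lies behind the power and type I error table (Protocol Table 6, SAP Table 2), which is described as using the specified testing sequence;
- how a programmer should carry out the recalculation that SAP 2.4.4 requires.

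**Working it through.** **Step 1. Fractions from Table 7.** NHS follow-up is 45 x 1.5 + 45 x 2.0 = 157.5 years, counted in full at every look. MOVE at completion is 80 x 2.0 = 160, so the total is 317.5. I read the 35 subjects with longer follow-up as part of the 80.

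| Look | MOVE years | Fraction | Printed |
|---|---|---|---|
| Interim 1 | 35 x 1.0 + 45 x 0.5 = 57.5 | 215/317.5 = 67.7% | 66% |
| Interim 2 | 35 x 1.5 + 45 x 1.0 = 97.5 | 255/317.5 = 80.3% | 80% |
| Interim 3 | 35 x 2.0 + 45 x 1.5 = 137.5 | 295/317.5 = 92.9% | 92% |

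The second agrees. The third differs by straight counting, but Table 7 marks its later counts as approximate. With eight enrolled per month, looks timed as planned and follow-up counted to the last six-monthly scan, 32 rather than 35 subjects have the longer follow-up at the second and third looks. That gives (157.5 + 32 x 1.5 + 48 x 1.0)/317.5 = 79.8% and (157.5 + 32 x 2.0 + 48 x 1.5)/317.5 = 92.4%, which match 80% and 92%. The first look stays at 67.7% under the same accrual, so 66% is unexplained.

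**Step 2. The named function.** Cumulative error spent is alpha(t) = 2[1 - Phi(z/sqrt(t))], with z = 2.2414 (the 0.9875 normal quantile). At 0.66, 0.80, 0.92 and 1 this is 0.00580, 0.01221, 0.01945 and 0.02500. Each nominal threshold is then solved so that crossing for the first time at that look uses exactly its increment, with correlation sqrt(t_i/t_j) between looks.

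**Step 3. A classical O'Brien-Fleming boundary.** Here z_k = c/sqrt(t_k), with one constant c chosen so that the overall one-sided error is 0.025. At the exact Table 7 fractions c = 2.0757, so the critical values are 2.522, 2.316, 2.153 and 2.076.

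| Boundary | Interim 1 | Interim 2 | Interim 3 | Final |
|---|---|---|---|---|
| Printed | 0.0058 | 0.0103 | 0.0156 | 0.0190 |
| Lan-DeMets at 66/80/92% | 0.00580 | 0.01050 | 0.01553 | 0.01843 |
| Lan-DeMets at 67.7/80.3/92.9% | 0.00645 | 0.01050 | 0.01606 | 0.01823 |
| Classical at 66/80/92% | 0.00533 | 0.01018 | 0.01527 | 0.01901 |
| Classical at 67.7/80.3/92.9% | 0.00583 | 0.01027 | 0.01564 | 0.01896 |

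Only the last row reproduces all four printed values to four decimals. Rounding of the percentages does not rescue the named function: fractions that round to 66/80/92 give a final threshold between 0.0183 and 0.0186. Pocock-type spending does not match either.

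**Step 4. Overall error of the printed set.** One-sided, by multivariate normal integration: 0.0253 at 66/80/92/100%, and 0.0250 (0.02501) at the Table 7 fractions. If the three printed interim thresholds are kept and the final one is set to use up the remaining alpha, it is 0.0185 at the printed fractions and 0.0190 at the Table 7 fractions.

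**The case against.** The strongest defence is that the decision numbers are right and only their description is loose. Step 3 supports this: the thresholds follow from Table 7's counts and hold 2.5% there. The SAP's own wording leans the same way, since its recalculation paragraph pairs the spending function with an O'Brien-Fleming boundary. That defence stands against any claim of inflated error, but it does not clear the text. For the printed thresholds to be right, both the named method and the printed 66% must be wrong. Changing the method alone, at 66/80/92%, gives 0.0053, 0.0102, 0.0153 and 0.0190.

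The second defence is that the figures are illustrative. SAP 2.4.4 ties them to a planning scenario, recalculates the thresholds at each look, and sets the final one to spend the alpha that remains. With 99 rather than 80 subjects enrolled, the planning fractions would not have applied in any case. After the futility crossing at the second interim analysis, the SAP applies no thresholds at all. This stands, and it limits the consequence. It is weaker for the protocol: the Synopsis and 8.5.2.1 give 0.9810 without the recalculation rule or the withdrawal of thresholds, and 8.7 refers back to 8.5.2.1 for the pre-specified values.

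A reader might infer that 0.0190 is too lenient and ought to be 0.0182 to 0.0184. That follows only if the named function is taken as what was actually used. The documents do not settle this, and the exact match in Step 3 makes a misnamed method with misprinted percentages at least as likely.

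**Conclusion.** The named function, the printed fractions and the printed thresholds are mutually inconsistent. Of the fractions, 66% does not follow from Table 7, 92% is attainable under the stated accrual though straight counting gives 92.9%, and 80% agrees.

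The size is small. If the printed percentages are taken as true, the printed set spends about 0.0003 too much; at the Table 7 counts there is no excess. If the named function is taken as true, the final posterior criterion would be 0.9816 or 0.9818 instead of 0.9810. The documents do not show that the trial's error rate was compromised.

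This rests on the stated definition of information (summed follow-up over 317.5 years), full NHS data at every look, and the usual normal approximation linking posterior probabilities to one-sided p-values. It is a minor documentation fault in a stated decision rule.

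**What to change.** First establish from the design records which boundary was computed and which was used in the power simulations. Then make the Protocol Synopsis, Protocol 8.2 and 8.5.2.1, and SAP 1.7, 1.9.1 and 2.4.4 (including Table 7 and the recalculation paragraph) agree, in one of two ways.

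- **(a) Classical boundary.** Name a classical O'Brien-Fleming boundary, print 67.7%, 80.3% and 92.9%, and keep the four thresholds and 0.9810. The recalculation paragraph then needs a rule that fits this boundary, because it now refers to the spending function.
- **(b) Lan-DeMets spending.** Keep the named function and print 0.0065, 0.0105, 0.0161 and 0.0182 (final posterior above 0.9818) at 67.7%, 80.3% and 92.9%. Alternatively print 0.0058, 0.0105, 0.0155 and 0.0184 (above 0.9816) at 66%, 80% and 92%, and explain where 66% comes from.

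The protocol should also carry the SAP's statements that thresholds are recalculated and that none is applied after the second interim analysis. The cost is a text correction and a check of records. Under (b) the final threshold tightens by 0.0006 to 0.0008. No current decision changes under either option.

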### 8.5.2 Analyses of Efficacy Endpoints

#### 8.5.2.1 Primary Efficacy Analysis

The primary efficacy endpoint is the annualized change in new HO volume (as assessed by low-dose WBCT) over 24 months in Part A. The change in new HO volume is calculated by summing the increase in HO volume across all body regions for which new HO has occurred, where the increase in HO volume per region is defined as the square root of the volumetric increase in that region. The change in new HO volume is modeled using a Bayesian compound Poisson distribution. The Bayesian compound Poisson distribution assumes that the change in new HO volume can be modeled as a compound distribution of the number of body regions with new HO,  $K$ , and the new HO volume per region where new HO has occurred. The number of body regions with new HO in subject  $i$  for WBCT scan  $j$  with duration  $w_{ij}$  (the time between scan  $j$  and the previous scan) is distributed as

$$K_{ij} \sim \text{Pois}(\lambda_i * w_{ij} * \theta_{1,t(ij)}).$$

The subject-level rate  $\lambda_i$  follows a gamma distribution and  $t(ij)$  is an indicator function equal to 1 if the subject was on treatment at the time of the  $j$ th WBCT scan and 0 if the subject was not on treatment. Letting  $\theta_{1,0} = 1$ , the variable  $\theta_{1,1}$  is the multiplicative effect of palovarotene treatment on the mean number of body regions with new HO. The new HO volume in region  $r$  where new HO has occurred for subject  $i$  in scan  $j$  is assumed to be distributed as

$$Z_{ijr} \sim N \left( \alpha * \alpha_r * \theta_{2,t(ij)}, \frac{\alpha_r^2}{\tau_{t(ij)}} \right).$$

Letting  $\theta_{2,0} = 1$ , the variable  $\theta_{2,1}$  is the multiplicative effect of palovarotene treatment on the new HO volume conditional on new HO occurring.

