The primary efficacy analysis comparing the annualized change in new HO volume between subjects treated with palovarotene and untreated subjects is performed by calculating the ratio of the annual mean change in HO volume in palovarotene treated subjects to untreated subjects using the Principal FAS and assuming missing at random. Using the Bayesian compound Poisson model described above, this ratio is calculated as the treatment effect on the rate of body regions with new HO,  $\theta_{1,1}$ , multiplied by the treatment effect on new HO volume conditional on new HO occurring,  $\theta_{2,1}$ , expressed as  $\gamma = \theta_{1,1} * \theta_{2,1}$ . Random samples generated via Gibbs sampling from the posterior distribution of  $\theta_{1,1}$  and  $\theta_{2,1}$  will be used to compute the posterior probability that  $\gamma < 1$  to determine statistical significance. The primary efficacy analysis described above will be repeated without the square-root transformation. Additional supportive analyses including the weighted mixed linear effect (wLME) analysis with and without the square-root transformation will also be performed.

Approximately 80 palovarotene-naïve subjects with the R206H ACVR1 mutation will be enrolled into the current study and will be followed for 2 years in Part A. There will be three early interim efficacy analyses and one final analysis in Part A. The first interim analysis will occur when 35 subjects complete 1 year of follow-up; the second and third interim analyses will occur when all subjects enrolled in the Principal EP have completed (ie, have WBCT data) 12 months and then 18 months of follow-up, respectively. The interim analyses will include the Month 6 WBCT results when that is the only observation available from a subject in the current study. While study success may be declared after one of the interim analyses or at the final analysis in Part A, all subjects will continue until completing 48 months of treatment.

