The primary efficacy analysis will be repeated using the Principal PPS. Further details regarding primary analysis and the planned sensitivity analyses are provided in the Statistical Analysis Plan. The primary efficacy endpoint will be summarized for the Supplementary FAS and PPS.

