For these reasons, while acknowledging that it is post-hoc, the sponsor believes that the Bayesian compound Poisson analysis without the square-root transformation is the more appropriate analysis of the primary endpoint, relative to the Bayesian compound Poisson analysis with the square-root transformation. The Bayesian analysis without square root transformation is referred to as the analysis of primary interest.

When performed without the square-root transformation, the new HO volume in region r , Z_{ijr} , where new HO has occurred for subject i in scan j is assumed to be distributed as:

$$Z_{ijr}/1000 \sim N\left(\alpha * \alpha_r * \theta_{2,t(ij)}, \frac{\alpha_r^2}{\tau_{t(ij)}}\right).$$

The prior distributions for the variables in this Bayesian compound Poisson distribution are the following:

$$\begin{aligned} \lambda_i &\sim \text{Gamma}(a, \text{scale} = b) \\ \beta_1, \beta_2 &\sim N(0, 2^2) \\ a, b &\sim \text{Gamma}(1, 1) \\ \alpha &\sim N(0, 10^2) \\ \alpha_r &\sim \text{Unif}(0, 4) \\ \tau_0, \tau_1 &\sim \text{Gamma}(1, 100) \\ \theta_{1,1}, \theta_{2,1} &\sim \text{Unif}(0, 2). \end{aligned}$$

The Bayesian compound Poisson model will be fitted using the R statistical computing language and environment. The R programs will be run using v3.5.0 or later; packages used, including version number, will be identified in the CSR.

Additional supportive analyses including the weighted mixed linear effect (wMLE) analysis with and without the square-root transformation will also be performed. The wLME analysis without the square-root transformation was previously the primary efficacy analysis, before the Bayesian compound Poisson analysis was added in Amendment 1 of the protocol. This wLME analysis without square-root transformation is referred to as the alternative analysis of primary interest.

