A subject-level random effect will be used to account for the correlation among repeated measures on the same subject as subjects may contribute follow-up from both the NHS and the current study. Baseline HO volume divided by age will be the only covariate included in the model, in addition to the factor identifying study of origin. The LME model will be fitted using only a subject's observations associated with the longest follow-up in the NHS and the current study with weights used to account for the different lengths of observed subject follow-up. Missing at random will be assumed for the primary analysis and no imputation of missing data performed.

The wLME analyses will be run using SAS 9.4 or higher. The code will use the following structure:

```
proc mixed data=data;
    class treat usubjid;
    model annrate_newho = treat basetot_bage /s;
    random usubjid;
    lsmeans treat/pdiff=control('0') cl;
    weight fup;
run;
```

In this code, treat is a binary indicator for study (1=MOVE, 0=NHS); usubjid is a unique identifier of subjects (used across all FOP studies); annrate_newho is the annualized rate of new HO; and fup is follow-up in years.

The Bayesian compound Poisson analysis and wLME analysis without square-root transformation and including all assessments on or before December 4, 2019, for subjects <14 years old on the date of their assessment and assessments on or before January 24, 2020, for all other subjects, will be repeated using the Principal PPS after the third interim analysis.

Descriptive statistics summarizing the total HO by study visit, change in HO volume by study visit, and change in HO volume from baseline by study visit will be provided. Tables summarizing annualized new HO will also be produced. Summaries will also be provided by body region. Summaries of new HO coincident with flare-ups and not coincident with flare-ups will also be generated. Summaries of annualized mean New HO, conditional on new HO volume>0 mm³, will be created. HO listings will also be generated.

Missingness, including frequency of WBCT not collected and regions that are not evaluable, will be summarized. Frequency of negative new HO, i.e., apparent reductions in HO overall and by body region (defined below), will also be summarized.

Handling of Reductions in HO

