The following sensitivity analyses will be conducted after the third interim analysis to examine the robustness of the Bayesian compound Poisson analysis without the square-root transformation, unless otherwise specified. All assessments on or before December 4, 2019, for subjects <14 years old on the date of their assessment and assessments on or before January 24, 2020, for all other subjects, will be used. Note that, given the consistency of results between the Bayesian compound Poisson and wLME analyses observed at the second and third interim analyses, the sensitivity analyses below will utilize both methodologies, as described. The results may be summarized jointly in forest plots, as appropriate.

To assess impact of differences between NHS and MOVE:

- Adjustment for additional baseline covariates: This sensitivity analysis will extend the primary efficacy analysis to include additional baseline covariates. These will include baseline HO volume divided by age, age, sex, months since last flare-up, and CAJIS. The palovarotene treatment effect will be estimated using the Bayesian compound Poisson distribution with all covariates included. A similar wLME will also be performed.
- Propensity score analysis: The propensity score, defined as the conditional probability of being treated given the baseline covariates, can be used to balance the baseline covariates across treatment groups.³ Therefore, it can reduce potential bias due to imbalances in the distributions of demographic and disease characteristics between the NHS and MOVE Trial. The propensity scores will be derived from a logistic regression model with the following covariates: baseline HO volume divided by age, age, sex, months since last flare-up, and CAJIS. Each subject's propensity score will be estimated from the logistic regression model, and subjects will be grouped by quartiles of their propensity scores. Propensity score quartile will be used as the only covariate in the Bayesian compound Poisson analysis. wLME will be conducted for each quartile and overall using the 5-level factor as a covariate (in addition to treatment).

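### The SAP omits the per-protocol run of the pre-specified square-root model that the protocol promises, and leaves three of its four Bayesian sensitivity refits on the untransformed scale only

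*SAP*

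**What the plan says.** Protocol 8.5.2.1 builds the primary efficacy analysis on a root scale: "the increase in HO volume per region is defined as the square root of the volumetric increase in that region". The untransformed fit appears there as a repeat of that analysis: "The primary efficacy analysis described above will be repeated without the square-root transformation". The section ends with a per-protocol commitment, "The primary efficacy analysis will be repeated using the Principal PPS", and a deferral, "Further details regarding primary analysis and the planned sensitivity analyses are provided in the Statistical Analysis Plan".

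SAP 2.4.4, under Additional Analyses, plans the per-protocol work as follows: "The Bayesian compound Poisson analysis and wLME analysis without square-root transformation and including all assessments on or before December 4, 2019" for subjects under 14 (24 January 2020 for the rest) "will be repeated using the Principal PPS after the third interim analysis". SAP 2.3 adds that no PPS analysis is planned after the interim CSR.

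Under Sensitivity Analyses, the same SAP section says the listed analyses "will be conducted after the third interim analysis to examine the robustness of the Bayesian compound Poisson analysis without the square-root transformation", with an allowance for items that specify otherwise. On the status of that model the SAP is open: "while acknowledging that it is post-hoc, the sponsor believes that the Bayesian compound Poisson analysis without the square-root transformation" is, in the sponsor's view, the more appropriate of the two Bayesian analyses.

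**The concern.** The two scales gave opposing answers at the second interim analysis. The square-root model crossed the futility boundary, meaning a posterior probability below 5% that γ < 0.7. SAP 1.4 reports the DMC's view that the transformation appeared to turn a conclusion of significant benefit into one of futility, and that such disparate results ruled out a confident conclusion about futility. The sponsor was then unblinded and came to prefer the untransformed Bayesian model.

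The control is external and non-randomised. Covariate adjustment, propensity scores and the per-protocol set are therefore the main planned checks on whether a result reflects imbalance or poor compliance. If these Bayesian checks are run on one scale only, a reader cannot tell whether the unfavourable pre-specified result would change under them, or whether the favourable post-hoc result is the more stable of the two.

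**Working it through.** No sample-size, power or alpha figure bears on this point. The check is a comparison of texts and a count.

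**Step 1: the per-protocol run.**

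| | Protocol 8.5.2.1 | SAP 2.4.4 and 2.3 |
|---|---|---|
| Model to be repeated in the PPS | The primary efficacy analysis, i.e. the square-root Bayesian model | Bayesian and wLME, both untransformed |
| Square-root runs in the PPS | 1 promised | 0 of 2 |
| Later PPS runs | – | None planned |

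The protocol calls the untransformed fit a repeat of the primary analysis, so that fit cannot be what the PPS sentence refers to. SAP 1.9, on changes to the protocol's statistical section, does not mention the PPS restriction. Nor does SAP 1.10, on changes between SAP versions; its V1.2 entry describes the sensitivity-analysis changes as clarifications.

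**Step 2: the sensitivity list in SAP 2.4.4.**

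| # | Analysis | Method | Square root named? |
|---|---|---|---|
| 1 | Additional baseline covariates | Bayesian, plus wLME | No |
| 2 | Propensity-score quartiles | Bayesian, plus wLME | No |
| 3 | Subjects with follow-up in both studies | wLME | No |
| 4 | Matched pairs | Paired t-test | No |
| 5 | Restricted follow-up | wLME | No |
| 6 | Tipping point | wLME-based imputation | No |
| 7 | GEE | GEE | No |
| 8 | Subgroups | Bayesian and wLME for new HO volume by age and age by sex; otherwise wLME or Fisher's exact test | No |
| 9 | Visit schedule (6-month data against data collapsed to annual) | Bayesian on both scales, plus wLME | Yes |

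Counts:
- Sensitivity list: 1 of 9 names the square root.
- List plus the PPS item: 1 of 9 + 1 = 10.
- Items that refit the Bayesian model (1, 2, 8, 9): 1 of 4.

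**Step 3: what the square-root scale receives elsewhere.** SAP Table 8 has ten rows. Three are square-root: Bayesian with the dosing-interruption cutoff, Bayesian with all timepoints, and wLME. The other seven are untransformed, including all four age-by-sex subsets. SAP 2.4.4 also plans five wLME series, of which series 3 (root of the whole-body sum) and series 5 (sum of regional roots) are square-root.

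**Step 4: what is missing.** The square-root Bayesian model adjusts only for sex and for age under or over 18. The root-scale wLME adjusts for baseline HO volume divided by age. No planned root-scale analysis adjusts for months since last flare-up, CAJIS or the propensity score, and none uses the PPS or the age subgroups.

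**The case against.** The strongest reply has four parts.

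1. *The protocol defers to the SAP on sensitivity analyses.* This stands. A reader might infer that the whole sensitivity plan breaches Protocol 8.5.2.1. It does not: the protocol lists no sensitivity analyses, so only the PPS item conflicts with it.

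2. *The square-root result is neither hidden nor abandoned.* This also stands. It has the runs in step 3, and Table 8 labels the all-timepoints root-scale row as the protocol-specified primary analysis. The SAP states that its own preference is post hoc and drops the success and futility thresholds for later efficacy analyses.

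3. *Most of the list does not test the post-hoc Bayesian model.* Largely correct. Items 3, 5 and 6 use wLME, item 7 uses GEE and item 4 a paired t-test. A reader might infer that every untransformed analysis was devised after unblinding. SAP 1.9.1 and 2.4.4 show that untransformed wLME was the primary analysis of the July 2017 protocol, although it returned as supportive only after the second interim analysis. The covariate item is also worded as an extension of the primary efficacy analysis, which leaves some ambiguity against the untransformed default in the lead-in.

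4. *The root scale is biased by the visit schedule, so more root-scale runs would mislead.* In the SAP's example, one 8000 mm³ event is split into two 4000 mm³ readings. Untransformed, the two effects cancel: 2 × (4000/8000) = 1. On the root scale they do not: 2 × (√4000/√8000) = 2/1.41 ≈ 1.41, against palovarotene. This is a reason to show root-scale checks on annual data beside the 6-month data, and the collapsed dataset is already planned. It is not a reason to omit them. The SAP itself warns that collapsing cannot undo the influence of interim scans on the reading process.

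It is also fair to say that a favourable post-hoc result is the one most in need of stress tests. That justifies running them on the untransformed scale, but not leaving them off the pre-specified one.

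**Conclusion.** Two findings of different standing.

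- **Protocol–SAP conflict.** The protocol promises a PPS repeat of the square-root Bayesian model. The SAP plans none, now or later, and does not record the change.
- **Selective robustness evidence, not a contradiction.** The Bayesian covariate-adjusted, propensity-score and age or age-by-sex subgroup refits default to the untransformed scale. Three of the four Bayesian sensitivity refits and eight of the nine listed analyses name no square-root version.

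The effect on the trial's estimate cannot be sized, because the documents give no results for any of these runs. The conclusion assumes that the lead-in default applies wherever an item does not name a scale, including the covariate item. It does not imply that the square-root results are suppressed, or that they would change under adjustment. The point should be addressed because it concerns the question on which the two scales disagreed.

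**What to change.** - In SAP 2.4.4, Additional Analyses, add the square-root Bayesian model to the Principal PPS run. At the least, record the departure from Protocol 8.5.2.1 and its reason in SAP 1.9 or 1.10.
- In SAP 2.4.4, Sensitivity Analyses, add the square-root model to the Bayesian covariate-adjusted, propensity-score and age or age-by-sex subgroup analyses.
- Show both scales side by side in the forest plots the SAP already allows, labelled pre-specified (square root) and post hoc (untransformed Bayesian).
- Give the root-scale results on the 6-month data and on the data collapsed to 12 months, and repeat the SAP's caveat about the reading process.
- Where a wLME-based check is shown on the root scale, use series 5, which the SAP pairs most closely with the square-root Bayesian model.

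The cost is SAP wording, repeat fits of an existing model and longer output. SAP 3.3 does not plan to rerun interim-CSR analyses, so these would be supplementary runs. Extending every item to the root scale is not proposed: tipping-point imputation, for example, would need a new definition there.
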